For the Part 3 expansion segment, the scan schedule will be at the end of every even-numbered cycle's rest period, and prior to starting the next infusion. The same methodology should be used for all assessments throughout the study. Assessments will be done using RECIST, version 1.1. Tumor

assessments will continue to be done after the patient discontinues from the study, until the criteria for progressive disease have been met, or the patient begins another cancer therapy, or withdraws consent.

For the Part 4 dose and schedule evaluation segment, tumor assessments will be performed from evaluation of a CT (chest/abdomen/pelvis) or an MRI scan obtained within 10 days of beginning Cycle 1 and approximately every 8 weeks thereafter (e.g. after completing the infusions of Cycles 2, 4, 6, etc).

4.1.7 **Adverse events**

An adverse event (AE) is any untoward medical occurrence in a patient administered a study drug, and that does not necessarily have a causal relationship with the study drug. (An AE can be any unfavorable and unintended sign or symptom, or disease temporally associated with the use of a study drug, whether or not related to the study drug.) Adverse events include any symptom, physical sign, syndrome or disease which either occurs during the study, having been absent at baseline, or, if present at baseline, appears to worsen during the course of a clinical trial, after starting treatment, whether considered treatment related or not.

Events involving adverse drug reactions, illnesses with onset during the study, or exacerbations of pre-existing illnesses should be recorded. Exacerbation of a pre-existing illness is defined as a manifestation (sign or symptom) of the illness that indicates a significant increase in the severity of the illness as compared to the severity noted at the start of the study. It may include a worsening or increase in severity of signs or symptoms of the illness, increase in the frequency of signs and symptoms of an intermittent illness, or the appearance of a new manifestation/complication.

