4.2.4.6 Rest Period, All Cycles, if needed (Cohort 11)

There is no mandatory or pre-specified rest period. If TK216 administration is paused, every seven days (± 1 day) after the TK216 infusion is stopped, the procedures listed below should be performed.

- Clinical laboratory tests (hematology);
- AE and concomitant medication assessment;
- The clinical laboratory testing may be done at a local laboratory, and the interview may be conducted by telephone.
- If the rest period is greater than 7 days ($+1$); an optional pre-dose PK sample may be requested.

When the patient re-starts, Day 1 assessments should be completed and continued eligibility should be assessed.

4.2.5 Early Termination/End of Treatment Visit, Cohort 11

For all patients in Cohort 11, an End of Treatment Visit will be conducted within 7 days after treatment discontinuation, and a Safety Follow-Up visit will be conducted approximately 28 days following the last day of TK216 infusion. The following procedures will be performed at the End of Treatment Visit:

- ECOG performance status
- Vital signs;
- Weight;
- For pediatric patients, height
- Complete physical examination;
- 12-lead ECG;
- Clinical laboratory tests (hematology, clinical chemistries, coagulation, urinalysis);
- Collect PD specimens (biomarker & PBMC);
- Urine pregnancy test: women of child-bearing potential only;
- If a CT scan or MRI has not been completed within 6 weeks, it should be done at this visit. The same method of assessing disease must be used throughout the study;
- Concomitant medication check;
- Adverse event assessment.

4.2.6 **TK216 Therapy Following Disease Progression (Part 4)**

Patients may rapidly develop tumor-related symptoms even in the face of stable or minimally progressive disease. Therefore, as of Protocol version 7.0, palliative local radiation therapy may be allowed if the following criteria are met:

1. Treatment is required for a symptomatic, non-target lesion(s) (example: pain due to compression of nerve in a closed space).
2. Planned radiation therapy is focal and the field does not involve the treatment of target lesion(s) directly or indirectly by an inability to fully shield adjacent target lesions from any radiation effect.
3. There is a reasonable possibility that the patient will benefit from additional systemic therapy with TK216.
4. Approval for this treatment has been granted by Oncternal.

4.2.7 **Post-treatment follow-up**

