A Safety Follow-Up telephone call will be conducted approximately 28 days following the last day of TK216 infusion, if the infusion is terminated early; or approximately 28 days after the completion of the last cycle which the patient completes. Additionally, each patient will be contacted by telephone or email approximately every 3 months following study discontinuation until death, loss to follow-up, or withdrawal of consent in order to assess disease progression and survival status. A review of the medical record may also be performed if applicable to assess disease progression and survival status.

4.2.8 **Patient withdrawal criteria and procedures**

A patient will be permanently discontinued from study treatment if the patient develops a toxicity or concurrent illness that, in the investigator's judgment, precludes further treatment with the study drug.

A patient may be permanently discontinued from the study for any of the following reasons:

- Intolerable adverse event that does not improve with dose adjustments

- significant abnormal clinical laboratory values that are possibly, probably or certainly attributed to study drug. This includes Grade 3 or greater laboratory abnormalities that do not improve to \leq Grade 1 or baseline severity within 4 weeks of the last dose received.
- pregnancy
- non-compliance (not completing all required assessments at required times, missing scheduled visits, high frequency of missed doses, refusing to complete duration of dosing) or protocol violation
- patient withdraws consent and refuses to participate in the study
- investigator's or sponsor's decision that withdrawal is in the patient's best interest
- termination of the study by the sponsor (see Section 10.7)
- RECIST, version 1.1-defined disease progression is observed

If for any reason, a patient is discontinued from study before the patient completes 1 cycle of treatment; all assessments outlined in the Flow Chart of Study Assessments in the Study Synopsis and listed in Section 6.3.10 are to be completed. The reason(s) for a patient's discontinuation of treatment or withdrawal from the study will be clearly documented in the source documents and on the CRF. Any patient who completes Cycle 1 will be considered to have completed the study.

7 Study Drugs

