9.7 Efficacy

A modified intent to treat (mITT) approach will be used for efficacy analysis, in which the mITT population will consist of all patients who receive at least a partial dose of study therapy (i.e., any portion of the continuous infusion). Tumor response rates will be summarized by dose group and for all patients who receive the RP2D, including those from the dose and schedule escalation and expansion phases. Responses will be classified as CR, PR, SD or PD according to RECISTv.1.1 criteria. Summaries will be based on the best response recorded up until disease progression. Patients who discontinue prior to the first protocol-scheduled response assessment post first infusion will be considered as non-responders in the primary efficacy analysis. Objective tumor response (CR or PR) will also be summarized, as will PFS, OS, DCR and duration of response and DCR. Time to event data will be summarized by Kaplan-Meier methods, including 25th, 50th (median) and 75th percentiles with point estimates and two-sided 95% confidence intervals, as well as number and percent of censored observations.

10 Statistical analysis

The statistical analyses will be reported using summary tables, figures, and data listings. Continuous variables will be summarized with means, standard deviations, medians, minimums, and maximums. Categorical variables will be summarized by counts and by percentage of patients in corresponding categories. All raw data obtained from the case report forms as well as any derived data will be included in data listings. All analyses will be based on the Safety Population, which will include all patients who receive any amount of study drug.

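### In Part 4 the non-responder rule in section 9.7 turns on when a patient stops, so a CR or PR documented on the End of Treatment scan is scored as a failure in the primary analysis

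*Combined protocol and SAP*

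**What the plan says.** ORR is the primary objective of Part 4 (section 1.4). Section 9.7 sets the efficacy population: "the mITT population will consist of all patients who receive at least a partial dose of study therapy". It then gives three scoring statements in sequence.

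- Categories: "Responses will be classified as CR, PR, SD or PD according to RECISTv.1.1 criteria". There is no not-evaluable class.
- Best response: "Summaries will be based on the best response recorded up until disease progression". It sets no cut-off at discontinuation.
- Non-response: "Patients who discontinue prior to the first protocol-scheduled response assessment post first infusion will be considered as non-responders in the primary efficacy analysis". The trigger is the time of discontinuation; whether a scan exists plays no part.

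Two other sections decide which scans a Part 4 patient has. Section 4.1.6.6 has imaging "obtained within 10 days of beginning Cycle 1 and approximately every 8 weeks thereafter". Section 4.2.5 places the End of Treatment visit within 7 days after treatment discontinuation and adds: "If a CT scan or MRI has not been completed within 6 weeks, it should be done at this visit".

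Section 9.3 sets the Part 4 decision: null ORR 5%, target ORR 25%, one-sided exact test at 0.025, 80% power, success with at least 4 responders among 21 evaluable patients. Neither section 9.3 nor section 2.5, which uses the same word, defines evaluable. Section 10.6 repeats the best-response sentence without any non-responder rule.

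**The concern.** A rule for early discontinuation normally exists to stop patients without tumor data from leaving the denominator. This one is keyed to timing, and the protocol itself generates scans after the trigger. Take a patient who stops for toxicity in week 6 and whose End of Treatment scan shows a PR. The best-response sentence gives PR. The next sentence gives non-responder, and it names the primary analysis. The plan states no reason for setting the documented response aside.

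The Part 4 threshold is four responders. A change of status in one patient is enough to reverse the conclusion.

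**Working it through.** **Can such a patient arise?** Inputs: baseline scan up to 10 days before Cycle 1 and first scheduled scan at about 8 weeks, i.e. Day 56 (section 4.1.6.6); End of Treatment scan if none within 6 weeks, i.e. 42 days, at a visit within 7 days of stopping (section 4.2.5).

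- Baseline scan 10 days before Day 1: the 6 weeks have passed from about Day 42 − 10 = 32. With the visit up to 7 days after stopping, this is reachable for a patient who stops from about Day 32 − 7 = 25.
- Baseline scan at the start of Cycle 1 and visit on the day of stopping: reachable from about Day 42.

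The window therefore opens between roughly Day 25 and Day 42, depending on the two dates, and closes at about Day 56. Every patient who stops inside it is a non-responder under section 9.7, whatever the scan shows.

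**Reproducing the plan's design.** With X ~ Binomial(21, p), P(X ≥ 4) = 1 − Σ(k = 0 to 3) C(21,k) p^k (1−p)^(21−k).

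- p = 0.05: 1 − (0.3406 + 0.3764 + 0.1981 + 0.0660) = 0.0189, within the 0.025 limit.
- p = 0.25: 1 − (0.0024 + 0.0166 + 0.0555 + 0.1172) = 0.808, matching the stated 80%.

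**Effect of one patient.** Suppose there are four responders, one of them seen only on the End of Treatment scan.

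| Scoring | Responders | ORR | One-sided exact p against 5% | Decision |
|---|---|---|---|---|
| All documented responses count | 4/21 | 19.0% | 0.0189 | success |
| Section 9.7 as written | 3/21 | 14.3% | 0.0849 | failure |

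The second p-value is P(X ≥ 3) = 1 − (0.3406 + 0.3764 + 0.1981) = 0.0849.

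**Illustrative effect on power.** Let q be the share of true responders who stop in the window and are scored as failures. The documents give no value; 5% to 15% is assumed here. The countable ORR is 0.25 × (1 − q).

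| q (assumed) | Countable ORR | P(X ≥ 4) |
|---|---|---|
| 0 | 0.2500 | 0.808 |
| 5% | 0.2375 | 0.771 |
| 10% | 0.2250 | 0.728 |
| 15% | 0.2125 | 0.681 |

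For scale, 0.25 × 21 = 5.25 responders are expected at the target rate, so q = 10% is about half a patient.

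**Why evaluable needs aligning with any repair.** If patients without a scan were regarded as not evaluable and replaced until 21 had scans, the threshold of 4 would in effect apply to more than 21 treated patients. With an equal chance of response in the added patients, P(X ≥ 4) at p = 0.05 is 0.0222 for 22 treated and 0.0258 for 23, the latter above 0.025.

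**The case against.** The strongest reply is that the text already has an answer. The non-responder sentence is the more specific one and names the primary analysis, while the best-response sentence governs summaries in general. Read together, the patient is a primary non-responder and the PR still appears in the summaries and listings. The rule is prespecified and can only lower the ORR. Those affected must be responding, stop for good within a few weeks, and show the response on an off-schedule scan. Section 2.6.2 provides for holds and two dose reductions before discontinuation is raised, so they will be few. All of this limits the size of the point. It does not explain why a response documented on a scan that the protocol calls for should count as failure.

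A reader might also infer more than the documents support:

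- *That a patient who finishes Cycle 1 and then stops without a scan escapes the rule*, because section 4.2.8 says "Any patient who completes Cycle 1 will be considered to have completed the study". That needs completing Cycle 1 to mean not discontinuing. On that meaning, a patient who stops in week 6 after an uninterrupted 28-day Cycle 1 would escape as well, and the PR would count. Both readings cannot hold together. Stopping treatment is the natural sense: section 4.2.5 speaks of treatment discontinuation, and section 4.2.8 separates it from withdrawal from the study.
- *That a patient still on treatment whose week-8 scan is missed drops out of the denominator.* The mITT definition keeps every treated patient, and one without a CR or PR is in effect a non-responder. The only opening is the undefined word evaluable in section 9.3.
- *That later scans make the Part 4 conflict wider.* Section 4.1.6.6 does say that "assessments will continue to be done after the patient discontinues from the study", but in the Part 3 paragraph, and the Part 4 paragraph does not repeat it. The End of Treatment scan has to carry the Part 4 case.
- *That Part 3 has the same End of Treatment conflict.* For Cohort 10 the scan at that visit is done only if one is due (section 4.2.3.2).

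**Conclusion.** The point holds in a narrow form. In Part 4, two adjacent sentences of section 9.7 give opposite results for a patient who stops before about week 8 and whose End of Treatment scan shows a CR or PR, and the one that governs the primary analysis discards the response. The window runs from roughly Day 25–42 to Day 56, and one patient can change success into failure.

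The firm results are the textual conflict and the effect of one patient on the decision. The power figures are not findings about this trial: they rest on an assumed share of affected responders. The error is conservative, so it threatens a missed signal and not a false claim of activity. The design of 21 patients and at least 4 responders reproduces and does not need to change.

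**What to change.** Replace the non-responder sentence in section 9.7 with:

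> All mITT patients are in the ORR denominator. Best response uses all post-baseline RECIST v1.1 assessments, including End of Treatment scans and any later scans, up to progression or start of another cancer therapy. Any mITT patient without a CR or PR so documented, including those with no post-baseline scan for any reason, is a non-responder.

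Align the word evaluable in section 9.3 (and where section 2.5 repeats it) with this denominator. Section 4.2.8 needs no edit for this purpose.

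The cost is a few sentences, with no added scans or patients and no change to the threshold. The one downside is that a few early responses with short follow-up will count.

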10.3 Safety analysis

All patients who receive any amount of study drug will be included in the safety analyses. All adverse events will be mapped to preferred terms and system organ classes using the MedDRA dictionary. Patient incidence of adverse events will be displayed by dose group and by system organ class. Adverse events will also be summarized by severity and relationship to study drug. Patient incidence of serious adverse events will also be summarized.

Laboratory parameters will be summarized using descriptive statistics at baseline and at each post-baseline time point. Changes from baseline will also be summarized. In addition, shift tables (i.e.,

CTCAE grade at baseline versus CTCAE grade at follow-up) will be provided to assess changes in laboratory values from baseline to follow-up.

10.4 Pharmacokinetics

Pharmacokinetic variables will be summarized by dose group and time point.

10.5 Pharmacodynamics

Pharmacodynamic variables will be summarized by dose group and time point.

